3 GENERAL ANALYSIS AND REPORTING CONVENTIONS FOR ANALYSES

This section discusses general policies to be employed in the analysis and reporting of the data from the study. Departures from these general policies are provided in the specific detailed sections of this SAP. When this situation occurs, the rules set forth in the specific section take precedence over the general policies

All continuous study assessments will be summarized overall and by time point (as applicable) using the descriptive statistics n, mean, SD, median, and range (minimum, and maximum). All of the categorical study assessments will be summarized overall and by time point (as applicable)

CONFIDENTIAL

Page 11 of 33

using frequency counts and rates of occurrence (%). Changes from baseline for continuous outcomes will be presented as their corresponding continuous measures for post-baseline visits. All study data will be listed by subject, and time point (as applicable).

No preliminary rounding will be performed; rounding will only occur after the analysis. To round, consider the digit to the right of the last significant digit: if <5, then round down; if ≥5, then round up. Means and medians will be presented with one more decimal place than the precision of the data. Standard deviations will be presented with two more decimal places than the precision of the data. Percentages will be presented with one decimal place. A percentage of 100% will be reported as 100%. Minimums and maximums will be presented with the same precision as the original data.

All analyses will be performed using the SAS System® version 9.4 or higher. The domain (Study data tabulation Model [SDTM]) and analysis (Analysis Data Model [ADaM]) data sets will be taken as input to the SAS programs that generate the report-ready tables, figures, and listings. The submission ready SDTM and ADaM datasets will be provided to the sponsor along with display deliveries.

The following conventions will be used throughout the study analysis:

- Time T0 is the time of first treatment (first gel application) with study drug.
- The date of first treatment with study drug is Day 1.
- Assessment visit times are defined by time of treatment administration.
- Baseline value is defined as the last valid measurement prior to the dosing of study treatment.
- The change from baseline will be calculated as post-baseline value minus baseline value. If either the baseline or post baseline value is missing, the change from baseline is set to missing as well.
- Pain intensity difference (PID) is to be calculated by subtracting the pain intensity at each time point from the pain intensity at time 0

$$PID_t = PI_t - PI_0$$

• The number of days in the study is computed as: [Date of study completion or withdrawal minus the date of first study drug administration] + 1.

4 STUDY ASSESSMENTS

4.1 Efficacy Evaluations

4.1.1 Pain Intensity

Prior to exercise to induce DOMS, pain will be assessed for both legs at rest and while standing using a 0-100 point paper VAS to exclude subjects with other pain.

Following exercise to induce DOMS, pain at rest and while standing will be assessed for both legs using a 0-100 point eVAS and a categorical pain scale to determine qualification for

CONFIDENTIAL Page 12 of 33

randomization and to identify the study leg (baseline assessment). All pain assessments will be recorded in the e-diary.

After randomization, pain at rest and while standing will be assessed for the study leg and the non-study leg using a 0-100 point eVAS at all post-study gel application time points in Period 1 (see Table 2 of Protocol). When study gel application and pain assessment occur at the same time point, pain assessments will be performed before study gel application.

The subject will rest quietly for at least 5 minutes before assessing pain at rest for the study leg and non-study leg (the study leg will be assessed first). The subject will sit for at least 5 minutes, then stand up and rate the worst pain caused by standing (the act of moving from a sitting to standing position) for the study leg and non-study leg (the study leg will be assessed first).

4.1.2 Visual Analogue Scale

The pain VAS, a unidimensional measure of pain intensity, is a continuous scale from 0 to 100 comprised of a horizontal line anchored by 2 descriptors, one for each symptom extreme: "no pain" (score of 0) and "worst possible pain" (score of 100). A paper version of the pain VAS will be used for pre-exercise pain assessments (see Appendix 1 of Protocol).

The pain eVAS is electronically displayed and is completed by the subject for baseline and each post-randomization pain intensity assessment by touching the point on the eVAS that represents their pain intensity. (A capture program will linearly convert the pixel touched to an integer between 0 and 100). The integers of the eVAS will be referred to as points. The assessment date and time for the study leg and for the non-study leg is recorded in the e-diary (see Appendix 1 of Protocol).

4.1.3 Categorical Pain Scale

A 4-point categorical pain scale (none, mild, moderate, severe) at rest will be used to assess pain intensity following the exercise session. A categorical pain scale is provided in Appendix 2 of Protocol.

4.1.4 Rescue Medication Use

Use of any rescue medication for DOMS is strongly discouraged until 168 hours after the first study gel application, at which time over the counter (OTC) acetaminophen (one 500 mg acetaminophen tablet twice daily, not more than every 6 hours) as rescue medication is permitted if required. Subjects experiencing severe pain, or inability to move or walk due to pain, may be permitted to use rescue medication (one 500 mg OTC acetaminophen tablet twice daily, not more than every 6 hours) prior to 168 hours after the first study gel application. If subjects take rescue medication within the first 168 hours after the first study gel application, it will be recorded in the ediary as rescue medication and entered into the eCRF as a concomitant medication and will be programmatically categorized as a concomitant medication. Subjects will record their pain intensity in the e-diary before taking the rescue medication. The number of tablets taken, and the date and time will be recorded in the e-diary.

CONFIDENTIAL Page 13 of 33

4.2 Safety Evaluations

Following safety evaluations will be performed. Refer section 9 of this SAP.

- Treatment emergent adverse event (TEAE) reports,
- · Laboratory test results,
- Vital signs,
- Physical examinations,
- ECG findings
- Skin Examination (Study gel application site reaction)
- Residue Evaluation

5 SUBJECT SUMMARIES

5.1 Analysis Populations

Analysis populations are defined as follows:

- Full Analysis Set (FAS) will include all randomized subjects who have a baseline pain score and at least 1 study gel applied. Subjects will be analyzed according to the treatment they are randomized to.
- The per-protocol set (PPS) will include all randomized subjects who have a baseline pain score, at least 1 study gel applied, and no major protocol violations. Subjects will be analyzed by treatment group according to the actual treatment received, i.e., "as treated".
- Safety set will include all subjects who have at least 1 study gel applied. Subjects will be analyzed by treatment group according to the actual treatment received, i.e., "as treated".

[figure not shown]
Analysis populations will be determined before final data base lock and study unblinding.

The primary and secondary efficacy analyses will be performed using FAS population. Efficacy analyses will also be carried out using PPS populations for selected endpoints as appropriate. Baseline characteristics will be summarized using FAS population and safety endpoints will be summarized using Safety population. All baseline characteristics and safety summaries will be presented by Treatment Arm and/or by Treatment assignment as specified below.

- Treatment Arm
 - o K-285
 - Menthol
- Treatment Assignment

K-285 1-weekK-285 3-week(K-285 3w

CONFIDENTIAL Page 14 of 33

5.2 Disposition of Subjects

The number of subjects screened, randomized, and treated will be summarized. The number of subjects discontinuing treatment/withdrawing from the study will be summarized along with the reasons for discontinuation/withdrawal. Subjects who are screen failures along with the inclusion/exclusion criteria and post-exercise inclusion criteria violation will also be summarized.

A listing of randomized and subject disposition will also be produced.

5.3 Protocol Deviations

Protocol deviations will be summarized, and all protocol deviations will be listed.

6 DEMOGRAPHIC AND OTHER BASELINE CHARACTERISTICS

6.1 Demographics and Baseline Characteristics

Demographic variables include age, sex, race, and ethnicity. Baseline characteristics include height, weight (kg), and body mass index (BMI; kg/m2). Demographics and baseline characteristics including identification of the study leg and baseline pain intensity of the study leg will be presented in a by-subject listing and summarized overall and by treatment group using FAS population.

For quantitative data, means, medians, standard deviations, minimum and maximum values will be determined. For qualitative data, counts and percentages will be calculated.

6.2 Medical History

Medical history including skin condition (history of rash, allergy, eczema, etc.) and any allergy history (including fragrance, jewelry, dust, clothing, house dust, animal, metal, rubber, nylon, food, pollen allergy, etc.), as collected at screening, will be coded using the Medical Dictionary for Regulatory Activities (MedDRA) version 21.0 and summarized by system organ class (SOC) and preferred term (PT) in a frequency table based on the safety population. The SOC and PT will each be sorted in descending order by overall frequency. Medical histories will also be presented in a by-subject listing using the coded and verbatim history terms.

AEs that occur prior to treatment or that are related to a medical history event will be captured as medical history prior to database lock.

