9.0 ADVERSE EVENTS

9.1 ADVERSE EVENT DEFINITION

An AE is any untoward medical occurrence in a subject administered a pharmaceutical product and which does not necessarily have a causal relationship with the pharmaceutical product. An AE can, therefore, be any unfavorable and unintended sign, symptom, or disease temporally associated with the use of a medicinal product, whether or not related to the medicinal product. Any worsening of the subject's disease under study or other medical conditions will also be considered to be an AE, unless it is within the normal range of disease fluctuation for that subject.

Clinically meaningful (for a given subject) changes in physical examination findings and abnormal objective test findings (e.g. clinical laboratory tests [except for elevated test results for serum CK, [Section 5.2.2.1](#)], ECGs) are also recorded as AEs. The criteria for determining whether an abnormal objective test finding should be reported as an AE are as follows:

1. test result is associated with accompanying symptoms, and/or;
2. test result requires additional diagnostic testing or medical/surgical intervention, and/or;
3. test result leads to a change in study dosing or discontinuation from the study, significant additional concomitant drug treatment or other therapy, and/or;
4. test result leads to any of the outcomes included in the definition of a serious AE (SAE).

Merely repeating a test, in the absence of any of the above conditions, does not meet condition number 2 above for reporting as an AE.

Any abnormal test result that is determined to be an error does not require reporting as an AE.

A TEAE is defined as an AE that begins after the start of study gel or an event that begins before the start of the study gel and worsens in intensity after starting treatment.

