9.2 REPORTING ADVERSE EVENTS

At each evaluation, the investigator will determine whether any AEs have occurred. The subject will be questioned in a general way and no specific symptoms will be suggested. If any AEs have occurred, they will be recorded on the AE pages of the CRF or eCRF and in the subject's medical record. If known, the diagnosis will be recorded, in preference to the listing of individual signs and symptoms.

Adverse event reporting begins when informed consent is obtained and ends at the conclusion of the study, unless an unresolved AE is still being followed.

The severity of the AE will be graded as follows:

| | |
|----------|---|
| Mild | The AE is easily tolerated and does not interfere with normal daily activities. |
| Moderate | The AE causes some interference with daily activities. |
| Severe | The AE causes all normal daily activities to be completely halted. |

The investigator will make a judgment regarding whether or not the AE was related to the study gel. (Please refer to the definitions below.) The investigator will evaluate any changes in laboratory values, make a determination as to whether or not the change is clinically important, and whether or not the changes were related to the study gel. However, even if the investigator feels there is no relationship to the study gel, the AE or laboratory abnormality **MUST** be recorded in the CRF/eCRF. The following guidance will be used by investigators when assessing relationship:

Related

- Occurs within a reasonable temporal sequence to administration of study gel or,
- Cannot be explained by concurrent disease or other drugs or chemicals or,
- Improves or disappears on stopping or reducing study gel (de-challenge)
- Reappears on repeated exposure to study gel (re-challenge)
- Is an unusual event that is known to be associated with the drug or this class of compound, and cannot be explained by other therapy or the participant's physical condition
- Unlikely to be attributed to concurrent disease or other drugs or a clinically reasonable response on withdrawal (de-challenge)

Unrelated

- Occurs with a temporal relationship to administration of study gel which makes a causal relationship improbable or,
- Other drugs, chemicals or underlying disease provide plausible explanations of causality or,
- Is known to be associated with the participant's clinical condition, or with other medication taken by the participant

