9.2 Adverse Events

Treatment-emergent AE is defined as an AE that begins after the start of study gel or an event that begins before the start of the study gel and worsens in intensity after starting treatment. Verbatim terms used by investigators to identify AEs in the CRFs will be mapped to the appropriate preferred (PT) and system organ class (SOC) using a standardized coding dictionary (MedDRA Version 21.0 or higher). All coding will be reviewed prior to database lock. All recorded AEs/SAEs and TEAEs will be summarized and listed for each treatment group.

In addition to a listing of all TEAEs, separate listings of subjects with SAEs and listings of subjects with severe, treatment related, and AEs leading to premature discontinuation will be provided.

An overall summary will be produced for each treatment group of both the number of events and the number of subjects with TEAEs, SAEs, TEAEs by severity, TEAEs by relationship to treatment, and TEAEs leading to premature discontinuation.

The incidence of TEAEs will be summarized for each treatment group by SOC and PT within SOC (sorted in descending order by overall frequency). These summaries will be given in separate tables for the following categories of TEAEs:

- All TEAEs
- TEAEs leading to premature discontinuation
- SAEs

Also summarized will be TEAEs by maximum severity and by maximum relatedness to treatment. Adverse events will be deemed treatment related if they were recorded as probably, possibly, or definitely related.

If a given subject experiences a TEAE that maps to the same PT more than once, the subject will be counted once for the PT at its greatest severity (i.e., mild, moderate, or severe) and causality (i.e., attribution to study medication).

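### SAP 6.2 allows AEs tied to medical history to be recoded as history with no onset limit, which conflicts with the AE and TEAE definitions

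*SAP*

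**What the plan says.** **Recoding rule.** SAP 6.2 (Medical History) states that "AEs that occur prior to treatment or that are related to a medical history event will be captured as medical history", and dates this step before database lock. The same section describes medical history "as collected at screening, will be coded using the Medical Dictionary for Regulatory Activities", and names rash, eczema and allergies among the conditions covered.

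**AE definition.** Protocol 9.1 says that worsening of the disease under study or of "other medical conditions will also be considered to be an AE, unless it is within the normal range of disease fluctuation" for that subject.

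**TEAE definition.** Protocol 9.1: "A TEAE is defined as an AE that begins after the start of study gel". It adds events that begin earlier and worsen. SAP 9.2 repeats both parts, the second being "an event that begins before the start of the study gel and worsens in intensity after starting treatment". Neither document makes an exception for events related to medical history.

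**Reporting.** SAP 9.2: "All recorded AEs/SAEs and TEAEs will be summarized and listed for each treatment group". Protocol 9.2 starts AE reporting at informed consent.

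**Underlying disease.** Protocol 9.2 lists among the reasons to judge an event Unrelated: "Other drugs, chemicals or underlying disease provide plausible explanations of causality". It also requires that "even if the investigator feels there is no relationship to the study gel, the AE or laboratory abnormality" be recorded.

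**Relatedness labels (minor point).** Protocol 9.2 gives two categories, Related and Unrelated. SAP 9.2 counts an event as treatment related if it carries one of three graded terms (possible, probable or definite), and analyses a missing relationship as related.

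**The concern.** The first half of the SAP 6.2 sentence is limited to events before treatment. The second half is not. The reference to database lock dates the recoding, not the event. A data manager who follows the sentence as written could therefore move a post-gel event out of the category in which protocol 9.1 and SAP 9.2 place it.

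This matters more here than in most trials. The product is a topical gel, application site reactions are a safety endpoint, and protocol 5.2.6 sends signs of skin irritation to the AE section of the eCRF. Protocol 1.2 reports application site erythema, pruritus, dryness and exfoliation among the commonest treatment-related events in the Phase 1 study. Events of that kind could plausibly be put down to a recorded history of eczema, rash or allergy. Safety and tolerability is a secondary objective, and it remains one for the 126 subjects who go into the final analysis after the futility stop (SAP 2.2.6).

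**Working it through.** The plan states no figure that bears on this point. The check sets the passages side by side and counts where an effect could appear.

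**1. What the second half of the sentence adds.** The rule has the form: recode if (A) the event is before treatment, or (B) it is related to a medical history event. An event that is both A and B is already covered by A. So B has a separate effect only on events not dated before treatment, that is, on events dated at or after first gel.

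**2. One event under each rule.** This example is hypothetical. A subject has eczema recorded at screening, and it flares on Day 3 beyond its normal fluctuation.

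| Rule | Result |
|---|---|
| Protocol 9.1, AE definition | AE |
| Protocol 9.1 and SAP 9.2, TEAE definition | Treatment-emergent |
| Protocol 9.2, causality | May be judged Unrelated; must still be recorded |
| SAP 6.2, second half | Medical history |

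The last row cannot be squared with the others unless the event is held in both places.

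**3. Does the SAP settle the conflict?** SAP 3 lets specific sections override its general policies. SAP 6.2 and 9.2 are both specific sections, so that rule does not choose between them.

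**4. When each type of data is collected (protocol Table 2).** The table has 11 schedule columns: Screening, Day -1, Day 1, Day 2, Days 3-8, Day 8, Days 9-14, Day 15, Days 16-22, EOS/ET and the follow-up call.
- Medical history is marked in 2 of 11 (Screening and Day -1), both before first gel.
- AE recording is marked in 11 of 11, of which 11 − 2 = 9 fall on Day 1 or later.

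**5. Where an omission would show (SAP 13.1.1).** The AE summary tables are 14.3.1.1.1, 14.3.1.1.2, 14.3.1.2.1, 14.3.1.2.2, 14.3.1.4.1, 14.3.1.4.2, 14.3.1.5.1 and 14.3.1.5.2. All 8 of 8 are titled as TEAE tables. A post-gel event held only as medical history would appear in none of them.

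**6. The first half of the sentence.** Recoding pre-gel AEs conflicts with reporting from consent and with the all-AE wording of SAP 9.2 and protocol 11.6. It leaves the 8 tables unchanged unless the event worsens after first gel. In that case the event is a TEAE, and the sentence does not exempt it.

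**7. Size.** The documents give no AE rates and no frequency of relevant history, so the number of affected events cannot be calculated. The counts in steps 4 and 5 show where the rule could reach, not how many events it would move.

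**The case against.** The strongest reply is that the second half of the sentence has a legitimate narrower meaning. Protocol 9.1 says that fluctuation within a subject's normal range is not an AE. An AE-page entry made after first gel for such a fluctuation is properly background. The same may be true of an entry for an old condition with no start date, because SAP 9.2 sets completely missing start dates to the day of first treatment. The authors may have meant only tidying of this kind. That stands as a plausible intention. It does not limit the sentence, which also covers true onset or worsening on gel.

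A reader might infer that recoded events will be deleted from the AE data. The documents do not say so. Being captured as medical history need not mean removal, and SAP 9.2 (all recorded AEs summarized and listed) and Listing 16.2.5.1 (Adverse Events) point the other way. The undercount is therefore conditional.

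A reader might also infer that the medical history record closes before first gel. Protocol 5.3.1, 6.3 and Table 2 give collection times only, and SAP 6.2 itself adds entries up to lock.

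Other safeguards are real. Skin examination scores are recorded separately and reported in Tables 14.9.1 and 14.9.2 and Listing 16.2.7.3. Subjects are aged 18 to 35 and screened for clinically relevant abnormalities, which limits relevant history. Recoding before lock may well be done blind: SAP 5.1 fixes the analysis populations before unblinding, although it does not say this of AE recoding. Blind handling would reduce the risk of bias between arms but would not prevent undercounting in both.

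On relatedness, a reader might infer that no event recorded as Related would ever count as treatment related. That would need an eCRF that uses the protocol's scale, which cannot be seen here, and a programmer who applies the SAP terms literally.

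**Conclusion.** The conflict in wording is real. As written, SAP 6.2 allows an AE that starts after first gel, or worsens then beyond normal fluctuation, to be recoded as medical history. Protocol 9.1, protocol 9.2 and SAP 9.2 require it to stay an AE with a causality judgment. The sentence should be corrected before lock.

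An effect on results rests on two assumptions: that the second half of the sentence is applied literally, and that recoded events are held only as medical history. If both hold, TEAE counts in the 8 planned AE summary tables would be too low by an unknown amount. The documents do not show that any event has been lost or that the arms would be affected differently. Scored skin findings would still be visible in their own outputs, though these do not replace the AE tables.

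The relatedness mismatch is minor and depends on the eCRF. If the eCRF uses Related and Unrelated, the output at issue is Listing 16.2.5.3 (Treatment Related Adverse Events). Total TEAEs and tables of relationship as recorded would not change.

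**What to change.** 1. **SAP 6.2.** Limit the sentence to events that start before first gel and do not worsen afterwards beyond normal fluctuation. Keep these in the AE data from consent, flagged as non-treatment-emergent.
2. **Post-gel events.** State that every AE that starts or worsens after first gel stays an AE with the investigator's recorded relationship, whether or not it is linked to medical history.
3. **Check before lock.** List every AE already captured as medical history, with its onset or worsening time against the time of first gel. Restore those that meet the TEAE definition.
4. **SAP 9.2 (minor).** Check the eCRF categories. If they follow the protocol, define treatment related as recorded Related or missing, which keeps the SAP's existing rule for missing values.

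The cost is an edit to two SAP sentences, one check listing and one mapping line in the AE program. No new data are needed. If the authors already intended the narrow reading of SAP 6.2, the edit only puts it in writing.
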